3. Adverse events will be reported to the UNC-CH IRB and to the NIH as required. Following UNC-CH Adverse Event guidelines, events that meet the criteria for an unanticipated problems involving risks to subjects or others (UPIRSO) and are also serious adverse events will be reported to the IRB within one (1) week of the investigator becoming aware of the event. Any other events that meet the criteria for a UPIRSO will be reported to the IRB within two (2) weeks of the investigator becoming aware of the problem. In accordance with the terms of the Federal Wide Assurance, the Office for Human Research Protections (OHRP) and the Federal Drug Administration (FDA) are notified in a timely manner of 1) serious or continuing noncompliance; 2) significant adverse events involving risk to participants or others; or 3) suspension or termination of IRB approval for a study. Unexpected problems involving risk, unless the event is serious and related to the research, are not routinely submitted to the sponsor.
4. Adverse events will be identified through clinical interviews, laboratory results, safety tests, and self-report questionnaires.
5. Every event will be reported to the principal investigator and [name] by the designated research associates and will be documented. An adverse event report will be generated for each even and will include a description of the event, when and how it was reported, and any official chart records or documentation to corroborate the event.
6. The adverse event report will also include the severity attribution of the adverse event using the Common Toxicity Criteria (CTC) scale: 0 = no adverse event or within normal limits; 1 = mild AE, not requiring treatment; 2 = moderate AE, resolved with treatment; 3 = severe AE, resulted in inability to carry on normal activities and required professional medical attention; 4 = life threatening or disabling AE; 5 = fatal AE.
7. The adverse event report will also include a determination of attribution according to the following scale: 0 = definitely not related; 1 = probably not related; 2 = possibly related; 3 = probably related; 4 = definitely related.

III. Safety Review Plan and Monitoring

Oversight of participant safety includes a review of adverse events as well as study progress, data integrity, and study outcomes.

A. Justification of sample size

We will have 80% power to detect a large effect size (.7) in 20 women. Our recently completed study of the effects of transdermal estradiol on mood symptoms in the same population showed a reduction in depressive symptoms with the PM-MDD group from pre-treatment to post-treatment ($t=4.3$, $p<0.001$ Cohen's $d=1.15$). We anticipate the TSEC (the active ingredient of which is estrogen) to have similar effects on mood symptoms, and thus, the sample size of 20 is a conservative estimate of the number of subject we will need to detect a statistically significant effect.

B. Safety and study progress reviews

1. The research coordinator will evaluate the study subjects at appropriate intervals and assess laboratory data and clinical signs for potential adverse events. The research coordinator will assist the PI with gathering information to help the PI determine classification and causality. The research coordinator will also observe and document all adverse events, act on the PI's recommendation, and maintain follow-up until reconciliation.
2. The principal investigator and [name] will review the adverse events, immediately after they occur, with follow-up resolution. The principal investigator and [name] will evaluate individual and cumulative participant data when making recommendations regarding the safe continuation of the study. The principal investigator will be notified within 24 hours of an adverse event.
3. Specific responsibilities of the principal investigator include:
 - a. Review the research protocol, informed consent documents, and plans for data safety and monitoring;
 - b. Evaluate the progress of the trial, including periodic assessments of data quality and timeliness, participant recruitment, accrual and retention, participant risk versus benefit, performance of the trial site, and other factors that can affect study outcome;
 - c. Consider factors external to the study when relevant information becomes available, such as scientific or therapeutic developments that may have an impact on the safety of the participants or the ethics of the trial;
 - d. Protect the safety of the study participants;
 - e. Report on the safety and progress of the trial;
 - f. Make recommendations to the UNC-CH IRB, and, if required to the Food and Drug Administration (FDA) concerning continuation, termination, or other modifications of the trial based on the observed beneficial or adverse effects of the treatment under study;
 - g. If appropriate, conduct interim analysis of efficacy in accordance with stopping rules which are clearly defined in advance of data analysis;
 - h. Ensure the confidentiality of the trial data and the results of monitoring; and,
 - i. Assist the UNC-CH IRB by commenting on any problems with study conduct, enrollment, and sample size and/or data collection.
4. The frequency of the principal investigator's review is detailed below:
 - Participant accrual—weekly
 - Study adherence and dropouts—Weekly
 - Adverse events—As events occur
 - Participant confidentiality—As events occur
5. The annual report will include a list and summary of any adverse events; whether the adverse event rates are consistent with pre-study assumptions; a summary of recruitment and retention and reason for dropouts; and whether the study is on track to be completed and accomplish the stated aims.

C. Stopping Rules—Individual Subject

Participants with significant clinical or laboratory abnormalities will be discontinued from the study prior to estrogen administration. Adverse mood symptoms will be monitored by administering the Hamilton Rating Scale for Depression (HRSD) at each study visit. If suicidal thoughts or severe mood symptoms are observed at any period in the protocol, then the HRSD will be administered on consecutive days for three days. Anyone scoring > 20 on the HRSD or expressing concerns about their ability to continue in the study, will be considered to have severe mood symptoms and be discontinued from the protocol. In the event of the occurrence of severe mood symptoms, the protocol will be terminated. Should this step prove to be unsuccessful, conventional medication will be prescribed as needed. Further, although we do not anticipate severe adverse reactions, we have arranged for inpatient hospital admission in the Psychiatry Department if symptoms are otherwise unmanageable.

IV. Informed Consent

Informed consent will be obtained from each subject at entry into the study. Potential participants will complete eligibility screening by telephone/online survey and by laboratory tests conducted at the first study visit. Prior to the eligibility screening, potential participants will give verbal consent via the phone or will read and agree to a consent statement on an online survey before providing any information. No more information will be asked of participants than necessary to obtain eligibility information and to contact those who appear eligible. [name], or her trained study staff, will obtain written informed consent from those individuals who pass the initial telephone or electronic screening and are interested in participating. During the consenting process, all of the applicable consent forms will be reviewed with each individual, and they will be given as much time as they would like to discuss their participation with their families and decide whether to participate.

V. Data Quality and Management

A. Measures to be taken to review data collection

1. Data will be collected and analyzed as specified in the protocol:

a. Study Design

Once determined eligible and physically well, participants will receive conjugated estrogens/bazedoxifene (Duavee) tablets (0.45 µg, 20 mg) for 3 weeks. fMRI sessions (described below) will take place at baseline and at the end of the third week of Duavee administration. In the first study visit, women will have a basic lab panel and serum pregnancy test performed. Prior to Duavee administration women will receive a pelvic exam, breast exam, and Papanicolaou test. Participants who can provide record of a pelvic exam and breast exam within the past year and normal pap results within the past 3 years will be permitted to decline the GYN exam. Women will be seen in the clinic each week during Duavee administration to assess blood levels of conjugated estrogens/bazedoxifene and mood symptoms.

Clinical Assessments. The SCID will be administered at baseline to determine study eligibility by [name] or her trained study staff. The following standard measures will be administered at baseline, both fMRI sessions, and weekly clinic visits: The Positive and Negative Affect Schedule is a 20-item questionnaire that measures both positive affect (PA) and negative affect (NA) and is sensitive to subtle changes in affect over time.

The Hamilton Rating Scale for Depression (HRSD) is a 21-item researcher-rated standardized scale that assesses depressive symptoms and is widely used as a measure of symptom change over time.

The Inventory of Depression and Anxiety Symptoms (IDAS) is a 64-item self-report questionnaire that comprehensively assesses anxiety and depression symptoms on 10 subscales. The IDAS has excellent psychometric properties and has been validated for assessing reproductive mood disorders.

The Mood and Anxiety Symptom Questionnaire – Anhedonic Depression Subscale (MASQ-AD) is a 22-item scale that assesses anhedonia (i.e., loss of interest and low positive affect). MASQ-AD scores have been associated with blunted striatal response to reward in previous studies of patients with depression.

The Greene Climacteric Scale (GCS) is a 21-item scale that is the gold-standard measure of four domains of climacteric symptoms: vasomotor, somatic, anxiety, and depression.

The Pittsburgh Sleep Quality Index (PSQI) is a 9-item questionnaire that measures the quality and sleep patterns in older adults.

The Hormone History Questionnaire is a 19-item inventory that assesses women's mental and physical health and was created for the purpose of this study.

The Trauma History Questionnaire is a 24-item measure that examines participant's experiences with potentially serious or traumatic life events.

fMRI Task and Protocol. The Monetary Incentive Delay (MID) Task engages reward circuitry during monetary incentive anticipation and outcomes. Each of two event-related MID runs consists of 90 6-second trials during which women will be presented with a cue shape, a fixation crosshair (for a variable duration), the target, and performance (win/loss/neutral) feedback. Cues indicate whether it is an incentive (gain, loss) or non-incentive trial. In incentive trials, women can either gain or lose money by pressing a button during target presentation, and difficulty is based on individual reaction times. This task elicits reliable frontostriatal dysregulation in people with remitted MDD³. Resting state scans will also be conducted.

FMRI Data Acquisition and Image Processing. Scanning is performed using a Siemens Magnetom 3T TIM Trio scanner. High-resolution, T1-weighted anatomical images will be acquired using an MPRAGE sequence. Whole-brain functional images will be acquired using a single-shot, gradient recalled echoplanar pulse sequence sensitive to blood-oxygen-level-dependent (BOLD) contrast. Each of 2 runs will consist of the acquisition of 195 successive brain volumes. FMRI image preprocessing, processing, and analysis will be conducted using FSL and custom MATLAB scripts. FMRI analyses will include an event-related BOLD response analysis within *a priori* structurally defined frontostriatal regions of interest (ROIs). Contrasts of interest will include win versus non-win outcomes, although the anticipation of wins will also be explored.

Probabilistic Reward Task (PRT) will be conducted outside of the scanner. This task allows us to test the additional hypothesis that perimneopausal depression is characterized by blunted reward learning. During this task, correct identifications of two ambiguous stimuli are differentially rewarded. The task will consist of 300 trials, divided into 3 blocks of 100 trials. Each trial starts with the presentation of a fixation cross for 500 msec followed by a mouthless face. After a delay of 500 msec, either a short mouth (11.5 mm) or a long mouth (13 mm) is presented for 100 msec. Participants will be asked to identify which type of mouth was presented. For each block, the long and short mouths are presented equally often in a pseudorandomized sequence and 40 correct trials are followed by reward feedback immediately after the correct response. An asymmetrical reinforcer ratio will be used in this task, such that for half of the participants, correct identification of the short mouth will be associated with three times more positive feedback (30 of 40) than correct identification of the long mouth (10 of 40). For the other half of the participants, the contingencies will be reversed.

The table below outlines the procedures that will occur at each study visit:

Assessments	1	2	3	4	5	6
Study visits	X	X	X	X	X	X
Consent	X					
OBGYN Exam		X				
fMRI			X			X
PRT			X			X
Venipuncture			X	X	X	X
SCID	X					
SNAP	X		X	X	X	X
HAM-D	X		X	X	X	X
IDAS	X		X	X	X	X
GCS	X		X	X	X	X
PSQI			X			X
HHQ						X
THQ						X
Duavee Rx Provided			X	X	X	
Payment	\$100	\$30	\$150	\$35	\$35	\$150

b. Statistical analysis strategy:

Aim 1: Determine the extent to which TSEC reduces anhedonia and other depressive symptoms in PM-MDD. Anhedonia and other depressive symptoms will be assessed at baseline and following 3 weeks of TSEC administration.

Null hypothesis (H_0): TSEC has no salutary effect on depression.

Alternative hypothesis (H_1): TSEC reduces depression as evidenced by 1) a statistically significant decrease in average MASQ Anhedonia scale score following 3 weeks of treatment, and 2) a clinically significant increase of 1 SD in MASQ Anhedonia scale score.

We will test this hypothesis using a paired t-test of MASQ Anhedonia scores at visit 1 (pre-treatment) and visit 6 (post-treatment).

Aim 2 (Exploratory): Quantify the effect of TSEC on the neural reward system in PM-MDD. We will use fMRI at baseline and following TSEC treatment in PM-MDD to probe

frontostriatal reward circuitry. We also will compare the effects of TSEC and ERT in PM-MDD.

Null hypothesis (H_0): TSEC has no meaningful effect on activity of the neural reward circuit in response to rewards.

Alternative hypothesis (H_1): TSEC reduces increases neural responsiveness to reward in the frontostriatal reward circuitry as evidenced by increased activation of the caudate, putamen, and nucleus accumbens in PM-MDD in response to reward following TSEC administration (compared with baseline).

We will test this hypothesis using a paired t-test to compare activity in 3 regions of interest (ROIs)—caudate, putamen, and nucleus accumbens—at the pretreatment and posttreatment scans.

2. The principal investigator will evaluate the progress of the trial, including periodic assessments of data quality and timeliness, participant recruitment, accrual and retention, participant risk versus benefit, performance of the trial site, and other factors that can affect study outcome.

B. Measures taken to insure data integrity and protection of databases

1. All study personnel are responsible for the collection and storage of data. All study staff participate in annual human subject training that includes education about responsibilities to minimize risk that confidentiality may be breached.
2. Participants will be identified by study ID number on all research documents and in electronic data files. All data will be stored in locked cabinets inside locked offices, and electronic data will be stored only on password-protected file servers only accessible from computers in the Psychiatry Department. Only study personnel will have access to these data. Qualtrics will be used to collect self-report questionnaire data for all participants with internet access. Participants will not enter any personally identifying information into the Qualtrics system, and they will be identified by their unique study ID only.
3. All members of the team will have access to the secure file servers on which electronic data are stored. It will be therefore unnecessary to send data files between investigators

VI. Confidentiality

As explained above, research subjects will be identified by their assigned study number on all research documents, electronic files, and specimen. Study documents will be stored in locked cabinets inside locked offices, and electronic data will be stored on secure servers accessible only on password-protected computers.

Santen, R. J., Allred, D. C., Ardoine, S. P., Archer, D. F., Boyd, N., Braunstein, G. D., ... Endocrine Society. (2010). Postmenopausal hormone therapy: an Endocrine Society scientific statement. *The Journal of Clinical Endocrinology and Metabolism*, 95(7 Suppl 1), s1–s66. ,
ACOG Practice Bulletin No. 141: management of menopausal symptoms. (2014). *Obstetrics and Gynecology*, 123(1), 202–216.

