1.4 Clinical Data to Date

We do not expect any adverse side effects associated with the hormonal manipulations outlined in this protocol for the following reasons: We will be administering estrogen paired with selective estrogen receptor modulators (SERMs) to a subset of women with perimenopausal women. SERMs are synthetic non-steroidal agents that have estrogen agonist and antagonist effects in different tissues, to block the negative effects of estrogen on non-target tissues, including the reproductive organs and cardiovascular system, while allowing estrogen to exert effects on target tissues like the brain, and thus decreasing risk for side effects.

Adverse Events Related to Combined Hormone Replacement and the Results of the Women's Health Initiative (WHI): The WHI study demonstrated that continuous administration of one form of estrogen (conjugated estrogens) in combination with one form of progesterone (medroxyprogesterone acetate) is associated with an increased risk of dementia, heart attacks, stroke, blood clots, and breast cancer. TSECs, the form of estrogen that we use in this study, is administered as a sole agent and, consequently, we do not expect that it will pose the increased risks observed with the chronic combination of the conjugated estrogens and medroxyprogesterone administered in the WHI study. Indeed, while the estrogen alone arm of the WHI trial was shown to be associated with an increased risk of stroke, no increased risk of either heart disease or breast cancer was observed^{55,56}. Estrogens may precipitate migraine headaches, and depression has also been reported to occur with the use of estrogens. In general, considering the dose and duration of treatment that we propose to use in this protocol, the risk of developing such side effects is negligible.

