Conjugated Estrogens/Bazdoxifene (Duavee): The first such tissue selective estrogen complex (TSEC) approved by the FDA is Duavee, which combines conjugated estrogens and the SERM bazedoxifene [1]. Bazedoxifene has antiestrogenic effects in the endometrium and breast, protecting against uterine and breast cancer, and estrogenic effects in bone, making it a potent preventive agent and treatment for osteoporosis. Duavee has been shown to alleviate hot flashes and vaginal atrophy and prevent osteoarthritis. The safety of conjugated estrogens/bazedoxifene was evaluated in four Phase 3 clinical trials (sponsored by Wyeth) ranging from 12 weeks to 24 months in duration and enrolling 6,210 postmenopausal women age 40 to 75 years (mean age 55 years). A total of 1,224 patients were treated with DUAVEE and 1,069 patients received placebo. The incidence of all-cause mortality was 0.0% in the DUAVEE group and 0.2% in the placebo group. The incidence of serious adverse reactions was 3.5% in the DUAVEE group and 4.8% in the placebo group, and 7.5% of the DUAVEE group and 10.0% of the placebo group withdrew [1]. The most common adverse reactions leading to discontinuation were hot flashes, upper abdominal pain, and nausea. Other less common adverse reactions included diarrhea, dyspepsia, muscle spasms, neck pain, dizziness and oropharyngeal pain [1]. The incidence of endometrial hyperplasia was less than 1% in both clinical studies examining the effect of Duavee on the endometrium [1, 2, 3, 4]. The SMART study examined safety and efficacy of Duavee and found that women reported low incidences of breast pain and high incidences of cumulative amenorrhea, in addition to relief of vasomotor symptoms [5].

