We do not expect any adverse side effects associated with the hormonal manipulations outlined in this protocol for the following reasons: We will be administering estrogen paired with selective estrogen receptor modulators (SERMs). SERMs are synthetic non-steroidal agents that have estrogen agonist and antagonist effects in different tissues, to block the negative effects of estrogen on non-target tissues, including the reproductive organs and cardiovascular system, while allowing estrogen to exert effects on target tissues like the brain, and thus decreasing risk for side effects.

Duavée: Nausea is the most common side effect of TSEC administration. At conventional replacement doses, higher than those employed in this protocol, this complaint seldom interferes with eating, and no weight loss has been reported. Abdominal pain, hot flashes, breast engorgement, endometrial hyperplasia and bleeding are also common side effects of TSEC administration. Pre-existing fibroid tumors of the uterus may enlarge under the effects of TSECs; however, at the dosage and for the duration of estrogen administration in this protocol this risk is small.

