The relationship between estrogens, both endogenous and exogenous, and the development of endometrial carcinoma has been suggested by several different lines of investigation. Numerous retrospective case control studies published since 1975 have indicated that post menopausal exposure to unopposed estrogens for more than one year results in a two to 12 fold increased relative risk for endometrial cancer. A relationship between the dose and duration of estrogen use and the risk for endometrial cancer has also been shown, the risk being increased after one to four years of estrogen use and rising also with the dosage employed. However, the addition of SERMS to estrogen replacement therapy appears to decrease the risk of endometrial hyperplasia and endometrial cancer to equal or below that of women receiving no hormonal treatment. There is an increased risk of thromboembolism in women receiving non-contraceptive estrogen therapy. Additionally, some but not all studies report an increase in risk of stroke, in older women taking estrogen therapy. However, these complications are unlikely at the dose and duration of estrogen replacement employed in this protocol and in the younger age group of women who participate in this study. Blood pressure, on average, appears to be unaffected by estrogen therapy, although both increases and decreases have been reported. In observational studies, post-menopausal estrogen therapy has been observed to lower the relative risk of cardiovascular disease in some but not all studies. In contrast, recent randomized controlled trials in older postmenopausal women (e.g., Women's Health Initiative [WHI]) report an increased risk of cardiovascular disease. Emerging data suggest that these disparities in findings may be related to the timing of initiation of estrogen therapy in relation to the proximity of menopause. Additionally, the increased risk of CHD was observed in older but not younger perimenopausal women. High doses of oral estrogens have been reported to elevate hepatocellular enzyme levels and, less commonly, cause cholestatic jaundice. The risk for gall stones and hepatocellular adenomas has been reported to be increased in association with oral contraceptive use, and although uncommon these complications may also occur with the use of replacement doses of estrogen. Estrogen therapy also may increase the risk of urinary incontinence in older postmenopausal women. Further, most studies have suggested an increased relative risk of breast cancer after four or five years' use, similar to the risk expected if the onset of menopause was delayed for a comparable length of time. Due to the publicity surrounding the cancellation of the treatment arm of the Women's Health Initiative study that involved the administration of combined conjugated estrogens and medroxyprogesterone acetate (Prempro), we have included the following statement in the consent documents:

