
Adverse Events Related to Combined Hormone Replacement and the Results of the Women's Health Initiative (WHI): The WHI study demonstrated that continuous administration of one form of estrogen (estradiol) in combination with one form of progesterone (medroxyprogesterone acetate) is associated with an increased risk of dementia, heart attacks, stroke, blood clots, and breast cancer. Conjugated estrogens, the form of estrogen that we use in this study, is administered with bazedoxifene, a SERM, that helps to prevent and, consequently, we do not expect that it will pose the increased risks observed with the chronic combination of the conjugated estrogens and medroxyprogesterone administered in the WHI study. Indeed, while the estrogen alone arm of the WHI trial was shown to be associated with an increased risk of stroke, no increased risk of either heart disease or breast cancer was observed. Estrogens may precipitate migraine headaches, and depression has also been reported to occur with the

use of estrogens. In general, considering the dose and duration of treatment that we propose to use in this protocol, the risk of developing such side effects is negligible.

Potential Benefits to Human Subjects

There is evidence suggesting that estrogens may serve as a therapeutic option for affective disorders in perimenopausal women. Thereby women who participate in the study may find that the estrogen therapy yields an improvement in symptoms related to mood or physical symptoms, and will have the option to continue hormone replacement after the study concludes. If a participant is interested in learning whether she demonstrated a differential susceptibility to the hormone replacement used in this study, she will be welcome to review the mood and physical symptoms that she experienced during the study with the PI.

B. Adverse event reporting

1. This study defines an unanticipated problem as an incident, experience or outcome that is both *unexpected* (in nature, severity, or frequency) and *related or possibly related to the research*.
2. This study defines a serious adverse event as fatal or life threatening, requires or prolongs hospitalization or results in significant or persistent disability or congenital anomaly/birth defect.

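### The WHI risk statement intended for the consent documents names an estrogen that the rest of the plan contradicts, and leaves the reason for its reassurance unfinished

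*Combined protocol and SAP*

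**What the plan says.** Appendix A (Data and Safety Monitoring Plan), Section II.A, Duavee Side Effects, refers to the publicity about the cancelled WHI treatment arm. It describes that arm as "the administration of combined conjugated estrogens and medroxyprogesterone acetate (Prempro), we have included the following statement in the consent documents". The paragraph that follows lists dementia, heart attacks, stroke, blood clots and breast cancer as associated with "continuous administration of one form of estrogen (estradiol) in combination with one form of progesterone (medroxyprogesterone acetate".

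Its second sentence says that conjugated estrogens are the estrogen used in this study and that they are given with bazedoxifene. It begins to say what bazedoxifene helps to prevent, breaks off without an object, and concludes that the investigators do not expect the "increased risks observed with the chronic combination of the conjugated estrogens and medroxyprogesterone administered in the WHI study". The paragraph then discloses the raised stroke risk in the estrogen-alone arm of WHI and closes with a general appeal to dose and duration.

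Section 1.4 (Clinical Data to Date) has a near-identical paragraph, but there the WHI regimen is "continuous administration of one form of estrogen (conjugated estrogens) in combination with one form of progesterone (medroxyprogesterone acetate", and the reason for expecting lower risk is that TSEC is given as the only agent. Section 1.2 describes the tablet as 0.45 mg conjugated estrogens with 20 mg bazedoxifene.

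On endometrial hyperplasia, Appendix A says that "endometrial hyperplasia and bleeding are also common side effects of TSEC administration". Section 1.4 says "The incidence of endometrial hyperplasia was less than 1% in both clinical studies" of the drug's endometrial effects. A later paragraph of Appendix A says that adding a SERM appears to bring the risk of hyperplasia and endometrial cancer down to, or below, that of women on no hormones.

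**The concern.** By the plan's own account this paragraph is told to participants and is not only background. Section 11 requires the consent form to give enough information for an informed decision.

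The order of the sentences matters. The reader first learns that estradiol with a progestin was associated with serious harm, and then that this study uses conjugated estrogens. A lay reader can easily take this to mean that the estrogen in her tablet is not the one studied in WHI. On the plan's other statements it is the same one. The slip therefore errs in the reassuring direction.

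A reader who looks for the actual reason finds a clause that stops before giving it. What is at stake is the accuracy and coherence of risk disclosure; the trial's estimates and tests are untouched.

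**Working it through.** No arithmetic applies. The check sets the statements side by side.

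**Step 1: which estrogen does the plan say WHI combined with medroxyprogesterone?**

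| Place | Estrogen named | Wording |
|---|---|---|
| Appendix A, WHI paragraph, first sentence | estradiol | "continuous administration of one form of estrogen (estradiol) in combination with one form of progesterone (medroxyprogesterone acetate" |
| Appendix A, WHI paragraph, second sentence | conjugated estrogens | "increased risks observed with the chronic combination of the conjugated estrogens and medroxyprogesterone administered in the WHI study" |
| Appendix A, lead-in to the paragraph | conjugated estrogens | "combined conjugated estrogens and medroxyprogesterone acetate (Prempro), we have included the following statement in the consent documents" |
| Section 1.4, parallel sentence | conjugated estrogens | "one form of estrogen (conjugated estrogens) in combination with one form of progesterone (medroxyprogesterone acetate" |

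One place says estradiol and three say conjugated estrogens. Section 1.4 also repeats conjugated estrogens in its own following sentence. The estradiol wording is the outlier, and its own paragraph contradicts it.

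**Step 2: which estrogen is in the study product?** Section 1.2 and the Appendix's second sentence both say conjugated estrogens. The study product and the WHI combination arm, as the plan describes them, therefore share their estrogen component. The type of estrogen cannot be a ground for expecting lower risk.

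**Step 3: does the reassurance depend on the wrong word?** Replace estradiol with conjugated estrogens and reread. The argument becomes: WHI gave conjugated estrogens with medroxyprogesterone; this study gives conjugated estrogens with bazedoxifene; so the WHI combination risks are not expected. The argument keeps its form. What the correction removes is only the suggestion that the estrogen differs.

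**Step 4: is the stated ground complete and consistent?** It is not complete, because the bazedoxifene clause names nothing that is prevented. Appendix A does say elsewhere that SERMs block unwanted estrogen effects in reproductive and cardiovascular tissue, but that is outside the paragraph designated for consent. It is not consistent either:

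- Appendix A rests on giving conjugated estrogens together with bazedoxifene.
- Section 1.4 rests on giving TSEC as the only agent. This may be meant as without a progestin, but as worded it does not fit a two-component tablet.

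**Step 5: hyperplasia.** The plan gives three descriptions: a common side effect (Appendix A), under 1% in the two endometrial studies (Section 1.4), and a risk no higher than without hormones (Appendix A, later paragraph). The first does not fit the other two.

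**The case against.** The strongest reply is that this is one wrong word, corrected one sentence later. The sentence that carries the reassurance attributes conjugated estrogens to WHI and gives bazedoxifene as the reason. The paragraph also discloses stroke risk with estrogen alone and refers to dose and duration.

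Much of that stands. A reader might infer that the reassurance is false because its premise is wrong. The documents do not support this: Step 3 shows that the express ground is not the type of estrogen, and nothing in the plan proves or disproves the expectation of lower risk. What does not stand is that the second sentence repairs the first. Two adjacent sentences that disagree do not reliably inform a lay reader, and the clause that should settle the matter is unfinished.

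A reader might also infer that the consent of all 20 women is compromised. The consent form is an attachment and was not in the text reviewed. Appendix A says only that the statement is included, so whether the form has the word estradiol or the broken clause is unknown.

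Finally, a reader might infer that calling hyperplasia common lets a case be treated as expected and go unreported. That is weak. Section 8.3.1 sends any type of serious adverse event to the PI and IRB within 24 hours, whether expected or not, and Section 8.3.2 makes a side effect more frequent than expected reportable. The under-1% figure stands in the protocol itself, which Section 8.1 counts among the documents for judging expectedness. Section 8.1 also requires seriousness. Under the definition in Appendix A, Section II.B, which does not, the label could matter only for non-serious cases. The hyperplasia wording also overstates risk, the opposite direction from the WHI slip.

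**Conclusion.** The WHI sentence in Appendix A is wrong as written, judged by the plan's other statements: three places against one, including the next sentence of the same paragraph. It can mislead a participant about whether her estrogen is the one studied in WHI. The reason for the reassurance is incomplete in Appendix A and different in Section 1.4. The expectation of lower risk is neither established nor refuted.

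This is an internal inconsistency in risk disclosure. It should be corrected because the text is said to reach participants. Its extent is conditional: up to the planned 20 women if the consent form repeats the wording, and none through this route if it does not. The conclusion assumes only that the plan's majority account of the WHI regimen is the intended one. The hyperplasia conflict is secondary.

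**What to change.** - In Appendix A, Section II.A, correct the estrogen in the first WHI sentence so that it agrees with Section 1.4, the lead-in and the following sentence.
- Complete the bazedoxifene clause so that it states what is thought to be prevented.
- Reconcile the ground in Section 1.4 (only agent) with the ground in Appendix A (given with bazedoxifene) and with the two-component tablet in Section 1.2. Make clear that any expected difference in risk does not rest on a different type of estrogen.
- Check the consent form for the same wording, and correct it through the IRB if it is there.
- Reconcile the three descriptions of endometrial hyperplasia in Appendix A and Section 1.4, and use one agreed statement of frequency throughout.

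The cost is a few sentences of redrafting and IRB review of the amended text. The design, sample size and analysis do not change.
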